STUDY PROTOCOL: THRIVE AND LARYNGOLOGIC SURGERY

1

**The Safety and Efficacy of the Transnasal Humidified Rapid-Insufflation Ventilatory Exchange (THRIVE)
for Short Laryngologic Surgical Procedures**

Study Protocol

NCT03091179

February 15, 2017

STUDY PROTOCOL: THRIVE AND LARYNGOLOGIC SURGERY

STUDY OBJECTIVES

1. DETERMINING THE SAFETY AND EFFICACY OF THRIVE FOR SHORT LARYNGOLOGIC SURGERY.

THRIVE should improve operating conditions, decrease surgical time, and potentially lead to better patient outcomes. The safety of THRIVE for short laryngologic surgery has not been formally investigated, and will be explored in this study. With the patient anesthetized, apneic, and adequately oxygenated with THRIVE, the build up of carbon dioxide in patient's blood (PaCO_2) and ensuing acute hypercapnic acidosis will be the main factors limiting the duration of THRIVE administration. At present, the rate of PaCO_2 rise with THRIVE has not been directly investigated, but is suggested to be between 1.1 and 1.8 mm Hg per minute. It is expected that the short duration of laryngologic procedures explored in this study (not exceeding 30 min) will not lead to substantial rise of PaCO_2 . The PaCO_2 rise to 75 mm Hg is considered a safe level for moderate hypercapnia in patients without significant comorbidities (see Exclusion Criteria).

2. DETERMINING POSSIBLE BENEFICIAL EFFECT OF THRIVE ON IMMEDIATE POSTOPERATIVE RECOVERY in PACU, QUALITY OF POSTOPERATIVE RECOVERY (QoR15), OPIOD CONSUMTION, AND VOICE HANDICAP INDEX (VHI-10).

EXCLUSION CRITERIA

1. Patients with significantly decreased myocardial function (ejection fraction < 50%)
2. Patients with abnormal cardiac rhythm and conduction abnormalities, except for patients with isolated, asymptomatic premature atrial and ventricular contractions.
3. Patients with significant peripheral vascular disease, such as those with the symptoms of intermittent claudication.
4. Patients with known significant cerebrovascular disease, such as history of cerebrovascular accidents (CVAs) and transient ischemic attacks (TIAs).
5. Patients with significant renal insufficiency, as manifested by estimated glomerular filtration rate (eGFR) < 60 ml/min/1.73 m².
6. Patients with electrolyte (K+, Ca++) abnormalities, as determined by the lab values outside of a normal range.
7. Patients with the history or symptoms of increased intracranial pressure or reduced intracranial compliance (e.g. headaches, nausea and vomiting, visual changes, mental changes).
8. Patients with skull base defects.
9. Patients with pulmonary hypertension who have pulmonary artery pressures above the normal range.
10. Patients with significant chronic obstructive or restrictive lung diseases, as manifested by known history of baseline chronic hypoxia and/or hypercapnia, and/or baseline room air SpO₂ < 95%.
11. Obese patients with BMI above 35 kg/m².
12. Patients with severe and poorly controlled gastroesophageal reflux disease despite medical treatment.
13. Patients with hiatal hernia and full stomach patients.
14. Patients on immunosuppressive medications.
15. Patient's refusal to participate in the study.
16. Patients who do not understand English or mentally handicapped.
17. Pregnant or breastfeeding patients.

STUDY PROTOCOL: THRIVE AND LARYNGOLOGIC SURGERY

PROTOCOL AT A GLANCE AND STUDY END-POINTS

1. Patients will be randomly assigned to either THRIVE or ETT (control group). Patient with supraglottic jet ventilation will also be included in ETT group, if JV requested by surgeon.
2. Anesthetic management is standardized for both groups.
3. Study end-points:
 - A. THRIVE GROUP
 - i. Total apnea time
 - B. BOTH GROUPS
 - i. Demographic, ASA class and airway exam data
 - ii. Anesthesia duration: from induction to awake (opening eyes to command)
 - iii. Surgical duration: from picking up suspension laryngoscope to laryngoscope withdrawal
 - iv. Apnea time: from induction to spontaneous ventilation
 - v. Extubation time: from surgery stop to opening eyes to commands
 - vi. Time to suspension: from picking up suspension laryngoscope to full suspension
 - vii. Number of required repositions/adjustments of suspension laryngoscope during surgery
 - viii. Lowest SpO₂
 - ix. Hemodynamic & Sedline profile
 - x. Total doses of anesthetic drugs used intraop, including vasopressors, etc.
 - xi. Intraop complications
 - xii. PACU recovery profile:
 - Time to AO x 4: from arrival to PACU
 - Time to PACU phase 2-ready: from arrival to PACU
 - Pain and PAS scores
 - IV and PO opioid requirements
 - PO non-opioid requirements (PO Tylenol)

STUDY PROTOCOL: THRIVE AND LARYNGOLOGIC SURGERY

- Shivering: incidence; IV Demerol requirements
- PONV profile (nausea and vomiting incidence); IV Zofran/Phenergan requirements

xiii. Immediate postop complications

xiv. Functional home recovery profile after surgery during first postop week

- Pain scores
- PO opioid requirements
- PO non-opioid (Tylenol) requirements
- QoR15
- Return to daily activities
- Return to work

xv. VHI-10 (Voice Handicap Index)

- Preop vs 1 month after surgery

STUDY PROTOCOL: THRIVE AND LARYNGOLOGIC SURGERY

OPERATING ROOM PREPARATION

1. All drugs, airway supplies, eye tape, per routine.
2. 5.0 MLT ETT.
3. Precut large Tegaderm for securing ETT to the chin in left corner of mouth.
4. Video laryngoscopy system: either a Glidescope or Storz CMAC system.
5. Monsoon JV with connection tubing for suspension laryngoscope, and full humidification set up.
6. Four channel Alaris pump with:
 - a. NS carrier at 50 ml/hr
 - b. Propofol drip
 - c. Remifentanil drip
 - d. Check to assure tight connections throughout
7. 20 ml NS syringe in-line for chasing the induction and IVP drugs intraop. **Please minimize IVF beyond 10 ml/kg total (5 ml/kg prior to induction, and 5 ml/kg as required intraoperatively), due to high incidence of urinary retention in male patients.**
8. Working PNS with pads (make sure the battery is fresh).
9. Sedline monitor.

STUDY PROTOCOL: THRIVE AND LARYNGOLOGIC SURGERY

	THRIVE GROUP	CONTROL GROUP
PREOP and PREMEDICATION	
 • Obtain patient's consent. Make 2 copies: one for the chart, and another for the patient. • Randomize the patient to either THRIVE or CONTROL group (5.0 MLT or supraglottic jet). Note: patient is blinded to the modality used. • Obtain preop VAS pain score, QoR15 and VHI. • Patient's folder contains: a copy of consent, postop diaries, QoR15, VHI, all stamped with patient's stickers, and 3 return, pre-stamped envelopes. Enter DOS and subject # in diaries, QoR15, VHI. • Study folder contains: consent, preop QoR15, VHI, intraop and PACU data collection sheets, all stamped with patient's stickers. Place patient's sticker on study folder. • Peripheral IV, 20 g R upper extremity (preferred), tape securely straight out. • Midazolam 0.007 mg/kg incremental doses to achieve sufficient anxiolysis, not to exceed 0.025 mg/kg total dose, unless severe anxiety. For elderly patients (70-80 y.o), limit total dose of Midazolam to 0.5 mg. 	
PRE-INDUCTION: CONSECUTIVE STEPS	
Start with OR table 180°.
 
Place standard ASA monitors, Sedline, and peripheral nerve stimulator (TOF ulnar nerve)
 
 • Pre-O₂ with THRIVE (FiO₂ 1.0) at 40 (30) l/min for 5 min. • Maintain patient's head is elevated 30-40° (table in BACK UP position, not reverse Trendelenburg). 	
OR table in standard position.
 
Preoxygenate for 5 min or until FeO₂ > 0.9.

	
 • IV fluid loading completed: 5 ml/kg. • IV Glycopyrrolate 0.2 mg if HR ≤ 50 bpm for elderly patients (70-80 y.o.). • Assure all surgical supplies are ready for immediate use in THRIVE group. • Both anesthesia and surgical time-outs completed. 	

STUDY PROTOCOL: THRIVE AND LARYNGOLOGIC SURGERY

INDUCTION	
 • IV Remifentanil 1 mcg/kg, Propofol 2mg/kg IV, Rocuronium 0.6 mg/kg IV, no IV lidocaine. • Additional Remifentanil 0.5 mcg/kg and/or Propofol 0.5 mg/kg IV boluses, as required during video or suspension laryngoscopy, per hemodynamic responses and Sedline readings. 	
	
 • Turn THRIVE to 70 l/min; mask ventilation if required. • Maintain jaw thrust, with oral airway as necessary, for 3 min, before surgeon starts suspension laryngoscopy. Continue, as necessary until patient is in full suspension. • Suspension laryngoscopy by surgeon in 3 min. 	
 • Mask ventilation. • Intubate when TOF is 0, with 5.0 MLT tube and video laryngoscopy (Glidescope or Storz CMAC), secure ETT to chin in left corner of the mouth. • If Jet is used, suspend when TOF is 0.
MAINTENANCE	
 • TIVA + THRIVE (FiO₂ 1.0) at 70 l/min. • NBP q 5 min, unless indicated more frequently. • If SpO₂ < 90%, or ventricular arrhythmias, discuss with surgeon converting to the following options: 
 ○ Supraglottic or Infraglottic HFJV ○ 5.0 MLT ○ 5.0 MLT with intermittent apnea technique • If surgical duration more than 30 min, institute supraglottic HFJV per THRIVE protocol, for at least 10 min. See jet settings in THRIVE protocol. 	

STUDY PROTOCOL: THRIVE AND LARYNGOLOGIC SURGERY

MAINTENANCE (cont.)	
 • Sedline-guided TIVA with Propofol/Remifentanil to maintain Sedline 25-50. • Maintain main IV at TKO. All IV bolus drugs are chased by 15 ml of NS using in-line 20 ml syringe. • TIVA dosing: 
 ○ TIVA is carried in by Alaris NS carrier at 50 ml/hr. ○ For normal weight patients, dose Prop/Remi infusions per total body weight. ○ For obese patients (BMI \geq 30), dose Prop/Remi infusions per lean body weight (LBW). Simplified LBW formula: LBW = IBW x 1.2; IBW = 22 x Ht(m)². ○ Starting dose: Propofol 120 mcg/kg/min, Remifentanil 0.1 mcg/kg/min. ○ Titratable range: Propofol 80-150 mcg/kg/min, Remifentanil 0.05-0.3 mcg/kg/min. Optimize Remifentanil dose first. ○ Rocuronium boluses 0.15 mg/kg, to maintain 0-1/4 TOF at ulnar nerve. • No IV Tylenol • Treating hypertensive responses (MAP > 20 mmHg from preoperative baseline): 
 ○ Remifentanil 0.5 mcg/kg and Propofol 0.5 mg/kg boluses q 2 min, as required per hemodynamic responses and Sedline readings ○ Labetalol 0.07 mg/kg boluses q 10 min up to a total dose of 1 mg/kg, as required per hemodynamic responses and Sedline readings ○ Fentanyl 0.5 mcg/kg IV bolus, total dose limit 1 mcg/kg, only if perceived need for additional analgesia after Remifentanil had been maxed out at 0.3 mcg/kg • Treating hypotensive responses (MAP < 20 mmHg from preoperative baseline): 
 ○ Crystalloid loading 5 ml/kg x 1 ○ Ephedrine 5 mg IV if HR < 60 bpm, or Phenylephrine 100 mcg IV if HR > 60 bpm. Repeat x 2 in escalating doses if no response: Ephedrine (10 mg, 20 mg q 1 min), or Phenylephrine (200 mcg, 400 mcg q 1 min). ○ Vasopressin 1 unit IVP if no response to Ephedrine/ Phenylephrine, repeat x 2 prn. ○ Phenylephrine drip, start at 0.3 mcg/kg/min, increase in 50% increments
EMERGENCE	
 • No IV Tylenol

STUDY PROTOCOL: THRIVE AND LARYNGOLOGIC SURGERY

10

	
• Zofran 4 mg IV.• Reverse NMB with Sugammadex, as following: 2 mg/kg for TOF 1-2/4; 4 mg/kg for TOF 0/4, with postetanic count of 1-2. Administer additional Sugammadex 2 mg/kg, if 4 mg/kg not fully effective.• Discontinue TIVA and disconnect TIVA line upon completion of surgery.• Transport to PACU: FMO₂ at 6 l/min.
	
• Maintain THRIVE at 70 l/min with jaw thrust ± oral airway as required, until return of spontaneous ventilation and consciousness.• Extubate per routine.
STANDARDIZED POSTOP ORDERS	
• Mild pain (1-3): Oxycodone 5 mg PO, may repeat x 1.• Moderate pain (4-6): Fentanyl 25 mcg IV q 5 min, for a total dose 3 mcg/kg.• Severe pain (7-10): Fentanyl 50 mcg IV q 5 min, for a total dose 3 mcg/kg.• Adjuvant analgesics: Tylenol 500 mg, may repeat x 1.• IV Demerol 12.5 mg for shivering only, may repeat x 1.• Treatment of PONV:
○ Zofran 8 mg IV x 1• If no effect, and no contraindications, add IV Promethazine 12.5 mg x 1
PACU DATA COLLECTION	
• Obtain PACU data collection sheet: Oriented x 4; Pain scores q 15 min; PAS scores q 30 min; Phase 2 ready.

STUDY PROTOCOL: THRIVE AND LARYNGOLOGIC SURGERY

THRIVE PROTOCOL	
PREOP	
• Randomize patient to THRIVE or CONTROL group. A control group is usually either a 5.0 MLT ETT or a Supraglottic HFJV.
PREINDUCTION	
• Pre-O₂ with THRIVE (FiO₂ 1.0) at 40 (30) l/min for 5 min.• Make sure the patient's head is elevated 30-40° (table in BACK UP position, not reverse Trendelenburg).
INDUCTION	
• THRIVE @ 70 l/min.• Maintain jaw thrust, with oral airway as necessary, for 3 min before surgeon starts suspension laryngoscopy. Continue jaw thrust as necessary, until patient is in full suspension.
MAINTENANCE	
• Maintain THRIVE @ 70 l/min.• If surgery prolonged (over 30 min), institute supraglottic HFJV for at least 10 min before switching back to THRIVE. Repeat as necessary.
○ HFJV settings:
▪ Frequency: 150 cpm▪ DP (driving pressure, psi) = total body weight x 0.4 (do not exceed 45 psi)▪ FiO₂ 1.0▪ Inspiratory time 40%▪ Humidity level: maximum (8)• 5.0 MLT can be placed by surgeon either instead of, or in conjunction with jet.
EMERGENCE	
• Maintain THRIVE at 70 l/min with jaw thrust ± oral airway as required, until return of spontaneous ventilation and consciousness. Mask (SGA) ventilation, as necessary.

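### At the protocol's own PaCO2 rise rates, 30 minutes of THRIVE apnea mostly overshoots its 75 mm Hg level, and no CO2 value is a listed end-point

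*Protocol*

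**What the plan says.** Study Objectives, item 1, makes four linked statements.

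- CO2 build-up and the resulting acidosis "will be the main factors limiting the duration of THRIVE administration".
- The rate of rise has not been directly investigated, but is "suggested to be between 1.1 and 1.8 mm Hg per minute".
- Procedures of at most 30 min are expected to be short enough that they "will not lead to substantial rise of PaCO_2".
- A reference level is then set out in these words: "The PaCO_2 rise to 75 mm Hg is considered a safe level for moderate hypercapnia in patients without significant comorbidities".

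No baseline PaCO2, projected PaCO2 or definition of substantial is given.

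Two clocks appear in the end-point list. Item B.iii has "Surgical duration: from picking up suspension laryngoscope to laryngoscope withdrawal"; item B.iv has "Apnea time: from induction to spontaneous ventilation". The THRIVE column of the Maintenance row ties the 30-min switch to jet ventilation to surgical duration. The Induction row has jaw thrust "for 3 min, before surgeon starts suspension laryngoscopy", and allows "mask ventilation if required".

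The only gas-exchange end-point listed is lowest SpO2. The conversion triggers in the Maintenance row are SpO2, ventricular arrhythmias and surgical duration. The SAP does not mention CO2.

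**The concern.** The duration and the rate stand in the same paragraph as the expectation and the 75 mm Hg level, and multiplying the first two does not readily give the third or the fourth. The protocol offers this reasoning to justify the 30-min duration under its safety objective.

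Measurement makes the problem worse. The hazard that the protocol ranks first has no listed end-point, so the published plan specifies no way to show whether 75 mm Hg was exceeded. Lowest SpO2 cannot stand in for it, because Objective 1 itself describes CO2 accumulating in a patient who is adequately oxygenated. A report that THRIVE was safe could therefore be read as covering hypercapnia when nothing in the listed data addresses it.

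**Working it through.** **Inputs from the protocol.** Rate r = 1.1 to 1.8 mm Hg/min, maximum duration 30 min and reference level 75 mm Hg (Study Objectives, item 1); 3 min between induction and suspension laryngoscopy (Induction row, THRIVE group).

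**Assumptions.** Baseline PaCO2 b is not in the documents; 35, 40 and 45 mm Hg are used. Exclusion criterion 10 removes patients with significant chronic lung disease shown by known baseline hypoxia or hypercapnia, so markedly raised baselines are not considered. The rise is taken as linear, with no CO2 clearance.

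The protocol prints no projected PaCO2, so there is no figure of its own to reproduce.

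**Step 1: rise over 30 min (no baseline needed).** 1.1 × 30 = 33; 1.8 × 30 = 54 mm Hg.

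**Step 2: comparison with 75 mm Hg.**

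- Value at 30 min = b + 30r.
- Break-even rate = (75 − b)/30.
- Share of the quoted range above break-even = (1.8 − max(break-even, 1.1))/0.7.
- Time to 75 = (75 − b)/r.

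| Baseline (assumed) | PaCO2 at 30 min | Break-even rate | Share of range above 75 | Time to 75 (r = 1.8 to 1.1) |
|---|---|---|---|---|
| 35 | 68-89 | 1.33 | 67% | 22.2-36.4 min |
| 40 | 73-94 | 1.17 | 90% | 19.4-31.8 min |
| 45 | 78-99 | 1.00 | 100% | 16.7-27.3 min |

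**Step 3: dependence on the baseline.** The highest baseline that stays at or below 75 at 30 min is 75 − 30r: 42 at r = 1.1, 31.5 at the mid-range rate of 1.45, and 21 at r = 1.8. So more than half of the quoted range passes 75 from any baseline above 31.5, and all of it from any baseline above 42.

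**Step 4: the clocks.** Apnea is counted from induction, about 3 min before the surgical clock starts. If no mask ventilation is used in that window, 30 min of surgery means at least 33 min of build-up. The rise is then 1.1 × 33 = 36.3 to 1.8 × 33 = 59.4, giving 71-94, 76-99 and 81-104 mm Hg from the three baselines. Any mask ventilation would clear CO2 and lower these values. Apnea also continues after laryngoscope withdrawal until breathing returns; that interval is not given and is not counted here.

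**Step 5: shorter procedures.** At 15 min from a baseline of 40, the value is 40 + 16.5 = 56.5 to 40 + 27 = 67 mm Hg, below 75 across the whole range.

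**The case against.** The strongest reply is that the protocol miscalculates nothing. It gives no projection, qualifies the rate as suggested, and calls 75 mm Hg a safe level without saying that higher values are unsafe or that 30 min keeps patients below it. The baseline and the reading of substantial as above 75 are supplied from outside. Thirty minutes is a maximum, the low end of the range can fit, and a share of an interval is neither a probability nor a proportion of patients. Standard ASA monitors are placed, intraoperative complications are recorded, and the intraoperative data sheet is not reproduced, so it might hold a CO2 field. The SAP calls the results exploratory.

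Much of this stands as a limit. The percentages describe the quoted range only and do not say how often 75 would be exceeded. The 33-min figures are conditional, and the conclusion does not need them.

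The core remains. The rise of 33 to 54 mm Hg needs no baseline and is hard to call insubstantial. If substantial is instead tied to 75, the only level offered, the mismatch covers most of the range at all three baselines. The expectation is stated for procedures up to the 30-min limit, so the limit is a fair test of it. Naming monitors and undefined complications specifies no CO2 value for collection, and an exploratory label does not supply one.

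**Conclusion.** The concern holds. At the protocol's maximum duration, its own rate range is inconsistent with the stated expectation and the 75 mm Hg level over most of its width: about two-thirds of the range at a baseline of 35 mm Hg, nine-tenths at 40 and all of it at 45. This rests on the assumed baselines, a linear rise without CO2 clearance, and reading substantial as above 75. It does not hold at the lowest rates from baselines of 42 or below, and it does not describe short procedures.

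The absence of a listed CO2 or pH end-point needs no assumption, although the fields of the unseen data sheet are unknown. Oxygenation and complications still inform the safety objective, and the other end-points are unaffected. This should be fixed; what it undermines is the hypercapnia part of the safety claim.

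**What to change.** 1. **Reconcile the passages in Study Objectives, item 1.** The duration, rise rate, expectation and 75 mm Hg statements need to agree. Compute the expected PaCO2 from the start of apnea, state the baseline assumed and define substantial. Which passage changes is for the investigators to decide.

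2. **List a CO2 value if one is obtainable.** In end-point list A (THRIVE group), beside total apnea time, add any CO2 reading available from monitoring already in use, with the apnea minutes at that reading. Note that an end-tidal value is an imperfect surrogate for PaCO2.

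3. **Otherwise narrow the claim.** If no reading is feasible, or data collection is over, limit the safety conclusion to oxygenation and recorded complications, and state that hypercapnia was not assessed.

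**Cost.** Items 1 and 2 need a wording amendment and one THRIVE-group data field. Item 2 may fail in practice: no CO2 monitor is named for that arm, and high flow continues until spontaneous breathing returns, so a clean end-tidal value may not be available. The SAP is written in the past tense, so collection may already have ended. Item 3 then costs one limitation sentence and a narrower safety claim.

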The Safety and Efficacy of the Transnasal Humidified Rapid-Insufflation Ventilatory Exchange (THRIVE) for Short Laryngologic Surgical Procedures

Statistical Analysis Plan

NCT03091179

June 20, 2019

Means and standard deviations were calculated for each of the patient characteristics. The statistical significance of differences between THRIVE and non-THRIVE patients was assessed using a *t*-test for all patient characteristics except gender, where a chi-square test was used. No adjustments were made to the statistical significance threshold for multiple comparisons, and our results should be viewed as exploratory.

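### Planned procedure is not listed, stratified on or adjusted for, which costs precision on surgical duration and VHI-10 and leaves a chance case-mix imbalance unseen

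*Protocol*

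**What the plan says.** **Eligibility.** Study Objectives, item 1, refers to "the short duration of laryngologic procedures explored in this study (not exceeding 30 min". The protocol gives no list of eligible operations, and all 17 exclusion criteria concern the patient, not the procedure.

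**Aims and end-points.** The same item expects that "THRIVE should improve operating conditions, decrease surgical time, and potentially lead to better patient outcomes". Item 2 names VHI-10 among the possible benefits. Under Protocol at a Glance and Study End-Points, both appear for both groups: item 3.B.iii, "Surgical duration: from picking up suspension laryngoscope to laryngoscope withdrawal", and item 3.B.xv, VHI-10, "Preop vs 1 month after surgery".

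**Data listed.** Item 3.B.i is "Demographic, ASA class and airway exam data". The preoperative row of the management table adds pain score, QoR15 and VHI. Procedure, lesion and diagnosis are not mentioned. The study folder holds "intraop and PACU data collection sheets", but their fields are not given.

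**Allocation.** "Patients will be randomly assigned to either THRIVE or ETT (control group") is the whole description apart from the reminders to randomise in the management tables. Ratio, blocking and stratification are not stated.

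**Analysis.** The SAP gives means and SDs, and a t-test "for all patient characteristics except gender, where a chi-square test was used". It names no test or model for surgical duration or VHI-10, and it describes the results as exploratory.

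**The concern.** How long a laryngoscope stays in place plausibly depends a good deal on the operation being done. The voice result at 1 month plausibly depends on the lesion and its treatment. The documents do not say so; it is a reasonable inference. The protocol does expect duration to vary, because its maintenance instructions provide for operations that run past 30 minutes.

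If the procedure explains part of these outcomes and is left out of the analysis, that part stays in the error term and widens the confidence interval. If the arms also differ in case mix by chance, the difference in means carries part of the case-mix difference. A reader working from the listed data could not see this or allow for it. At stake are the surgical-time claim in objective 1 and the voice claim in objective 2.

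**Working it through.** The documents give no sample size, SD, effect size, power or significance level, so there is no figure of theirs to reproduce. What follows is an illustration.

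**Assumed inputs (none from the documents).** 1:1 simple randomisation; two procedure types, half of patients each; type means b within-type SDs apart, with b = 0.5, 1 or 2; n = 20, 30, 50 or 100 per arm; two-sided 5% test.

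**Step 1: precision.** In within-type SD units, the total variance is 1 + b²/4. Adjustment removes the b²/4, so the required N falls to 1/(1 + b²/4) of the unadjusted N.

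- b = 0.5: 1/1.0625 = 0.94
- b = 1: 1/1.25 = 0.80
- b = 2: 1/2 = 0.50

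These factors ignore the small cost of estimating one coefficient, so the real saving is slightly less. As an example, with n = 30 per arm, b = 1 and a true effect of 0.6 within-type SD, power rises from 54.7% to 64.2% on the same approximation.

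**Step 2: chance of an imbalance.** The difference between arms in the proportion of one type has SD √(2 × 0.25/n). The exact binomial probability of a difference of 20 percentage points or more is:

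| n per arm | SD of difference | P(20 points or more) |
|---|---|---|
| 20 | 0.158 | 26.8% |
| 30 | 0.129 | 15.5% |
| 50 | 0.100 | 5.7% |
| 100 | 0.071 | 0.6% |

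**Step 3: consequence.** Simulation used 20,000 trials per setting with no true THRIVE effect. Over all randomisations, the unadjusted t-test rejected in 4.8% to 5.3% of trials. In the trials with an imbalance of 20 points or more, it rejected as follows:

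| n per arm | b = 0.5 | b = 1 | b = 2 |
|---|---|---|---|
| 20 | 5.7% | 9.7% | 14.1% |
| 30 | 6.4% | 11.9% | 20.8% |
| 50 | 7.5% | 14.4% | 33.1% |

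The rate grows with n because the standard error shrinks while the imbalance stays at 20 points or more; such imbalances also become rarer. In the same nine settings, the test adjusted for procedure type rejected in 3.9% to 5.7% of the imbalanced trials.

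**The case against.** The strongest reply is that chance imbalance is ordinary sampling error and the unadjusted test already allows for it. That is correct on average. A reader might build a striking case: types averaging 10 and 25 minutes, within-type SD 5, 20 per arm. The between-type variance is (15/2)² = 56.25 and the total is 56.25 + 25 = 81.25, so type explains 69% of it. Case mix then shifts the arm difference with an SD of 0.158 × 15 = 2.37 minutes. But the unadjusted standard error, √81.25 × √(2/20) = 2.85 minutes, already contains that shift: the within-type part is 5 × √(2/20) = 1.58, and √(1.58² + 2.37²) = 2.85. The 69% also follows from choosing types 3 SD apart, which nothing in the documents supports. The argument from bias therefore falls. The loss of precision and the error conditional on an observed imbalance remain.

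Four further points limit the claim.

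- A reader might infer that the SAP tests the end-points with unadjusted t-tests. It states those tests for patient characteristics only; the end-point analysis is unspecified.
- A reader might infer that the procedure is not recorded. The intraoperative sheet may hold it. What the documents support is that it is not listed.
- Preoperative VHI-10 is collected. A change score deals with baseline differences, but not with different expected improvement by operation.
- It is tempting to extend the point to time to suspension and number of repositions. Nothing in the documents shows that procedure type drives either.

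The exploratory label lowers the severity. It does not let a reader see or correct an imbalance.

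**Conclusion.** The point holds as one of efficiency and interpretability. The plan neither lists the planned procedure nor describes any use of it in allocation or analysis, although two both-group end-points plausibly depend on it. The documents do not support a claim that the comparison is biased or that its overall type I error is inflated.

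The size cannot be derived from the documents. Under the assumed two-type model, the precision gain runs from slight (types 0.5 SD apart) to a halving of the required N (2 SD apart), and it hardly depends on the trial's size. The imbalance risk does depend on size: it is material at 20 or 30 per arm and negligible at 100. VHI-10 was not quantified separately; the results carry over to it only if procedure types differ in expected voice change by a similar number of SDs. Severity: minor to moderate.

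**What to change.** 1. Assign each patient to one of two or three planned-procedure categories, taken from the operating list as it stood before allocation. This assumes such a list exists and can be retrieved. Use the planned procedure, since the one performed could be affected by the allocated technique. Whoever assigns the category should know neither arm nor outcome.
2. Show the category by arm in the patient-characteristics table.
3. In the SAP, specify a linear model for surgical duration with arm and category, and one for 1-month VHI-10 with arm, category and preoperative VHI-10.
4. Stratify randomisation by category only if allocation is still open. The SAP is dated June 2019, more than two years after the protocol, and is written in the past tense, so adjustment is probably the only route left.

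The cost is one extra field and two simple models. The downside is that the categories must be few and fixed without reference to arm or outcome; many small categories would use up degrees of freedom, and late choices would invite selective adjustment.

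### The protocol says patients are blinded to the modality, but the awake set-up before induction differs by arm and no concealment step is described

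*Protocol*

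**What the plan says.** In the protocol's management table, the Preop and Premedication row follows the instruction to randomize with one sentence: "Note: patient is blinded to the modality used". No method is given. The SAP does not mention blinding.

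The Pre-induction row then sets out different care for the two arms. THRIVE-arm patients are preoxygenated with THRIVE "at 40 (30) l/min for 5 min", on a table turned 180°, and the "head is elevated 30-40" degrees. Controls have the table in the standard position, and the instruction is "Preoxygenate for 5 min or until" FeO₂ exceeds 0.9. The control device is not named.

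Midazolam premedication is listed once for both groups, with the stated aim "to achieve sufficient anxiolysis, not to exceed 0.025 mg/kg total dose, unless severe anxiety". For patients aged 70-80 the total is limited to 0.5 mg.

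Objective 2 looks for a beneficial effect of THRIVE on PACU recovery, QoR15, opioid consumption and VHI-10. The end-point list includes a "Functional home recovery profile after surgery during first postop week", and VHI-10 before surgery and at 1 month.

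**The concern.** A patient who is still awake in the THRIVE arm experiences the modality under test. A patient in the control arm, as far as the text goes, does not. A flat statement that patients are blinded therefore claims a property that the described procedures do not provide.

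What is at stake is how Objective 2 is read. Pain scores, QoR15, return to activities and work, and VHI-10 all rest on what the patient reports. PACU opioid orders are set by pain-score band (1-3, 4-6, 7-10), so opioid use partly inherits any effect on the scores. Patient blinding is the only masking that the documents claim for these outcomes. A reader who trusts the note would rule out expectation as an explanation for a difference, without a documented basis for doing so.

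**Working it through.** No calculation in the plan bears on this point, so the check sets the procedures side by side where the patient is not anesthetized.

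**1. Before induction (main evidence)**

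| Feature | THRIVE arm | Control arm |
|---|---|---|
| Oxygen delivery | THRIVE, 40 (30) l/min, 5 min | Device not named; 5 min or FeO₂ > 0.9 |
| Table | Turned 180° | Standard position |
| Head | Up 30-40° | No elevation stated |

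All of this comes before the Induction row, where the first anesthetic drugs are listed. The THRIVE preoxygenation and the head position are repeated in the separate THRIVE Protocol table, so their assignment to that arm does not depend on the layout of one row. The table orientation appears only in the main table.

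**2. Emergence (secondary support only)**

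THRIVE continues at 70 l/min "until return of spontaneous ventilation and consciousness"; the other entry is "Extubate per routine". The first is repeated in the THRIVE Protocol table. Reading the second as the control entry is an inference from the fact that the planned THRIVE technique uses no tube. Return of consciousness is also where the THRIVE instruction stops, so the text does not establish any real period of aware exposure. The conclusion does not rest on this step.

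**3. Search for concealment**

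I looked in both documents for sham flow in controls, a common preoxygenation set-up, a rule on what patients are told after surgery, masking of the staff who collect PACU or home data, and a check of which technique patients believe they had. None is described.

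**4. Outcomes exposed**

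- Dependent on patient report: PACU and home pain scores, QoR15, return to activities, return to work, VHI-10.
- Partly dependent: PACU opioid use (keyed to pain score) and home analgesic use.
- Largely independent: surgical duration, time to suspension, apnea time, lowest SpO₂.

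**5. Can a bias be sized?**

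Let p_T and p_C be the proportions who infer their arm, and d_T and d_C the average shifts in their reports as a result. The between-arm difference in means then moves by p_T·d_T − p_C·d_C. The documents give none of these four quantities, nor the sign of either shift. Neither size nor direction can be derived.

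**The case against.** The strongest reply has five parts.

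- **The note may be an instruction to staff.** It sits in a preop checklist straight after randomization and may mean only that staff do not disclose the allocation. This stands as a possible reading, and it is why the remedy is a clarification. It does not help a reader who takes the sentence at face value.
- **Noticing a set-up is not knowing the arm.** Each patient experiences one set-up, and nothing in the documents says that patients are told which one belongs to which arm. The consent form and diaries are not available to settle this. It stands against any claim that patients were in fact unblinded. It does not show that blinding was secured.
- **Midazolam may blunt recall.** Possibly, in both arms. Its stated aim is anxiolysis, given in increments, and the protocol does not present it as a masking measure.
- **The modality can change under anesthesia.** A THRIVE patient may be converted to jet ventilation or a tube, and a control may receive either. A patient therefore cannot know everything that was used. But expectation would attach to the randomized technique, and that is what differs while the patient is awake.
- **The results are exploratory.** The SAP says so, and the only analysis it describes compares patient characteristics. This lowers the stakes. The SAP ties the label to unadjusted multiple comparisons, however, and the label does not make the blinding statement accurate.

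A reader might go further and infer that patients knew their arm, or that Objective 2 is biased in favor of THRIVE. The documents support neither: recognition is possible but not shown, and the direction of any effect is unknown.

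**Conclusion.** The point holds in limited form. As written, the design asserts patient blinding but does not secure it, because the awake pre-induction set-up differs by arm in oxygen delivery, table orientation and head position, with no concealment described. Actual unblinding is not shown.

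This rests on two assumptions: that controls are not preoxygenated with THRIVE (the device is unnamed, but THRIVE is not mentioned in their column), and that the consent form and diaries contain no concealment measure. If either fails, the point weakens or falls.

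The importance is minor to moderate. It affects how the patient-reported outcomes of Objective 2 may be described and read, from PACU through the first week to 1 month. It leaves the Objective 1 timings and SpO₂ largely untouched.

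**What to change.** 1. Qualify the blinding statement in the report, and in the protocol if it is amended again. Suggested wording: *Patients were not told their allocation; because the set-up before induction, while patients were awake, differed by arm, patient blinding is not assured.* Use the first clause only if the sponsor confirms it.
2. Report and interpret pain scores and the analgesic use keyed to them, QoR15, return to activities and work, and VHI-10 as not reliably patient-blinded.
3. If the consent form or diary contains a concealment step or a question on perceived allocation, cite it beside the blinding statement.
4. Only if follow-up is still open, add one question on perceived technique to the diary already in use and tabulate the answers by arm. The SAP of June 2019 is written in the past tense, so follow-up is probably closed; items 1 to 3 are then the whole remedy.

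No change to any clinical step is asked for. The cost is a sentence or two of text. The downside is a weaker claim for the patient-reported outcomes of Objective 2.
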